with poor well-being and psychosocial functioning (12), risk of suicidal behaviors (13) and overweight status (14, 15). Because of decreased financial resources of the families, increasing sedentary life styles and poor eating habits, adolescents are more likely to experiment adverse health conditions. Eating disorders (e.g., anorexia, binge eating, and eating disorders without other specification) and obesity are more likely to occur during adolescence (16). Portugal has one of the highest overweight prevalence rates in Europe (17). Several studies have pointed a paradoxical association between household food insecurity and overweight status in children (14, 15).

In the project *E-therapeutic intervention program for obese adolescents and their family*, funded by the Foundation for Science and Technology (PTDC / DTP-PIC / 0769/2012) and coordinated by [name], an e-platform was developed aimed to support and to manage adolescent obesity (Next.Step). The preliminary results showed that the platform is effective in promoting healthy behaviors, suggesting the relevance of technological tools as catalysts of behavioral change in Portuguese adolescents. So, based on our previous knowledge on e-intervention tools for adolescents, we intend to design a new platform and an app to promote healthy life styles, and promote food security as well as prevent disordered eating including obesity among adolescents.

Research on the association between food insecurity and well being in adolescence is scarce. Little is known about the effectiveness of interventions to reduce food security by promoting healthy life styles and psychological well-being and preventing disordered eating. Based on the literature search, we hypothesized that: (i) At 3 and 6 months adolescents will show lower indicators of food insecurity compared to the indicators of food insecurity at baseline; (ii) psychological well-being variables mediate the relationship between food insecurity and disordered eating.

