### 6. Project design

We will perform an interventional study on food security, psychological wellbeing and healthy eating using a sample of Portuguese adolescents. An e-platform, an app and specific psycho-educative sessions will be developed to support this study.

About 300 community adolescents from two schools will be invited to participate in a study. The intervention length is 6 months: (i) three months of direct intervention; (ii) evaluation at baseline, month 3, and follow-up at month 6.

- (i) Evaluation at baseline (T0)
- Application of validated questionnaires;
- Collection of anthropometric measures;
- Introduction to the use of the platform and the app;
- One psycho-educative session on healthy life styles for adolescents and another for parents.
- (ii) Evaluation at 3-months (T1)
- Application of validated questionnaires;
- Collection of anthropometric measures;
- One psycho-educative session for adolescents and another for parents. The psycho-educative sessions will focus on the discussion of the strategies to improve health lifestyles which have meanwhile been developed in the platform and the app some of them by the adolescents themselves.
- (iii) Evaluation at 6-months (T2)
- Application of validated questionnaires; collection of anthropometric measures.

The interactive e-platform and app will allow for the delivery and collection of information; discussion of nutritional and physical activities; share of solutions and strategies; favor cohesion among adolescents; promotion of behavior change. Psycho-

educative sessions will play an important role for discussing potential strategies to promote change.

The same validated questionnaires will be applied at T0, T1 and T2. Our team will apply robust statistical methods. The trial will follow the principles of best clinical practices, all adolescents and their parents will sign an informed consent and all procedures will be submitted to an Ethics Committee and to *Ministério da Educação* – *Monitorização dos inquéritos em meio escolar*.

Our aim is to assess the short and long-term change in clinical endpoints. This study has a high likelihood of success attending to the vast expertise of the team members involved in handling large studies, psychosocial variables assessment, interventions with adolescents, development of psycho-educative sessions, and management of group dynamics.

To accomplish our aims, this project comprises the following tasks:

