### 8.3. Task 3: Perform the study

In Task 3, we will conduct a longitudinal study with a mixed design. The intervention will last 3 months. Adolescents will be followed over 6 months.

Baseline, 3-month and 6-month evaluations will be conducted to collect anthropometric data (BMI, waist circumference and fat mass) and to apply validated questionnaires to adolescents and parents. In order to evaluate the economic determinant of food security, parents will answer to the food security questionnaire. Adolescents will answer to:

- Socio-demographic questionnaire;
- Physical and eating health questionnaire, adapted from Health Behaviour in Schoolaged Children (2010) and from Project Eat (18) (to evaluate the contextual determinants of food security);
- Nutrition questionnaire (NUT-Q, Raich et al., 2008);
- Eating Attitudes Test-26 (EAT-26; Garner & Garfinkel, 1979);
- Contour Drawing Rating Scale (CDRS; Thompson & Gray, 1995);
- EADS-21 (Lovibond & Lovibond; validated by Pais-Ribeiro, Honrado, & Leal 2004)
- Adolescent anthropometric data (weight, height, BMI, waist circumference and fat mass).

In each classroom, an identification of the group leader will take place with the purpose of facilitating adherence.

In both, platform and app, adolescents can choose to use a nick name to protect their identity. The adolescents will be presented to life situations and simulated cases and will be stimulated to present specific strategies directed to the promotion of food security and healthy lifestyles based on the cases presented. Adolescents will be motivated to comment the suggested strategies among them.

Culinary tips including healthy and low cost meals and physical activity tips will also be included. Adolescents will be stimulated to experiment these contents and comment on them.

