# 8.4. Task 6: Evaluation of the impact of the intervention and development of the final report, production of scientific papers and dissemination of the results

This task is dedicated to the organization and systematization of all collected information and results, aiming at the evaluation of the impact of the intervention and at its dissemination for the scientific community. The program effectiveness evaluation will result in a final report on strategies for the prevention of food insecurity and disordered eating, and for the promotion of well-being in adolescence.

We plan to deliver four manuscripts to be submitted to peer review journals (ISI indexed).

- (a) Study 1. The data collected in T0 will be used for the first manuscript. The manuscript will be a quantitative and transversal study. We will identify: adolescents with food insecurity; and variables associated with food insecurity. We schedule its submission in November 2016.
- (b) Study 2. The data collected in T0 will be used for the second manuscript. The manuscript will be a quantitative and transversal study and will focus on the relationships between food insecurity, well-being and disordered eating. Specifically, we aim to test whether well-being is a mediator variable

- between food insecurity and disordered eating; and whether sex is a moderator variable. We schedule its submission in December 2016.
- (c) Study 3. The data collected in T0 will be further used in the third manuscript. This manuscript will be a quantitative and transversal study and will focus on the impact of adolescents' family SES in food security, well-being and disordered eating. We schedule its submission in December 2016.
- (d) Study 4. In the fourth manuscript, we will use the data collected on-line (suggestions and reflections) during the 3-month intervention. The manuscript will be a qualitative study and will focus on the strategies pointed by the adolescents to motivate other adolescents to prevent food insecurity. We schedule its submission in March 2017.

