### 11.2. Statistical methods

Quantitative analysis will be performed with SPSS and AMOS. In the quantitative analysis, continuous variables will be reported as mean and standard deviation. Qualitative analysis will be performed with NVivo program.

In Study 1, we will perform clusters analysis in order to identify adolescents with food insecurity. In Study 2, we will perform structural equations modeling in order to analyze whether well-being is a mediator variable between food insecurity and disordered eating, and whether sex is a moderator variable. Multilevel analysis will be performed in Study 3. In Study 4, in order to analyze the qualitative data we will conduct Thematic Analysis (NVIVO program). Finally, in Study 5, we will conduct repeated-measures factorial ANOVASs for each variable; the analyses will be complemented with multiple comparisons using Bonferroni adjustment at p < .05.

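### The mediation hypothesis is tested on baseline data alone, which can show an association consistent with mediation but cannot establish it

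*Protocol*

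**What the plan says.** Section 4 of the protocol states two hypotheses. The second is that "psychological well-being variables mediate the relationship between food insecurity and disordered eating".

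Section 8.4 assigns the test to Study 2 and fixes the data: "The data collected in T0 will be used for the second manuscript. The manuscript will be a quantitative and transversal study". The stated aim there is still to test mediation. Section 11.2 gives the method: "we will perform structural equations modeling in order to analyze whether well-being is a mediator variable between food insecurity and disordered eating". Section 11.2 names no wave, so the restriction to T0 comes from reading it with Section 8.4.

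The constructs are measured repeatedly. Section 6 says: "The same validated questionnaires will be applied at T0, T1 and T2". For the baseline, 3-month and 6-month evaluations, Section 8.3 says that "parents will answer to the food security questionnaire", and its list for adolescents includes the "Eating Attitudes Test-26". Section 5.5 makes change in psychological well-being at 3 and 6 months a secondary endpoint. The only analysis given all three waves is Study 5, a repeated-measures ANOVA of the programme's impact, which does not address mediation.

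**The concern.** Mediation is a statement about order: food insecurity alters well-being, which in turn alters disordered eating. When all three are measured once, the order is put in by the analyst and the data cannot check it. An indirect effect that differs from zero is also what one would see if disordered eating lowered well-being, or if a common cause drove both.

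At stake is one of the protocol's two stated hypotheses. If Sections 8.4 and 11.2 are followed as written, Study 2 could report well-being as a mediator on evidence that does not separate this from the swapped order.

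**Working it through.** **Inputs from the protocol.** T0 data only for Study 2 (Section 8.4); structural equation modelling (Section 11.2); 300 adolescents in 6 classes from each of two schools, so 12 classes and 300/12 = 25 per class (Sections 6 and 11.1); end of follow-up in March 2016 (Section 10); Study 2 submission in December 2016 (Section 8.4). The protocol gives no correlations or path sizes, so those below are assumptions, with signs set so that all are positive.

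Write X for food insecurity, M for well-being and Y for disordered eating.

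**1. Model with a direct path.** Three observed scores give 3 × 4/2 = 6 variances and covariances. The model X→M→Y with X→Y has 3 paths, 1 variance and 2 residual variances, so 6 parameters and 6 − 6 = 0 degrees of freedom. The swapped model X→Y→M with X→M also has 6 parameters and 0 degrees of freedom. Both reproduce the data exactly. Latent variables add degrees of freedom to the measurement part only. The structural part still has three paths for three covariances, so the swap does not change the fit.

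**2. Model without a direct path.** This leaves 1 degree of freedom.
- X→M→Y implies r_xy = r_xm × r_my.
- The swap X→Y→M implies r_xm = r_xy × r_my, a different constraint, so these two can be told apart.
- The full reversal Y→M→X implies r_xy = r_xm × r_my again, so it fits exactly as well as the hypothesis.

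**3. Size of the indirect effect in the two orders (model with a direct path).**
- Hypothesised: r_xm × (r_my − r_xm × r_xy)/(1 − r_xm²)
- Swapped: r_xy × (r_my − r_xm × r_xy)/(1 − r_xy²)

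| Assumed r_xm, r_xy, r_my | Hypothesised | Swapped |
|---|---|---|
| 0.25, 0.30, 0.50 | 0.25 × 0.425/0.9375 = 0.113 | 0.30 × 0.425/0.91 = 0.140 |
| 0.30, 0.30, 0.30 | 0.30 × 0.21/0.91 = 0.069 | 0.069 (equal by symmetry) |

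**4. How often mediation would be declared when it is absent.** Simulation with 300 independent pupils and 2,000 runs. The truth is X→Y→M with equal standardised paths p, so well-being has no effect on disordered eating. The fitted model is the hypothesised one with a direct path, and mediation is declared when both component paths are significant at two-sided 0.05. Here r_xy = r_my = p and r_xm = p², so the expected spurious indirect effect is p³/(1 + p²).

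| Assumed p | Expected p³/(1 + p²) | Simulated mean | Mediation declared |
|---|---|---|---|
| 0.2 | 0.008/1.04 = 0.0077 | 0.0075 | 10.8% |
| 0.3 | 0.027/1.09 = 0.0248 | 0.0249 | 35.8% |
| 0.4 | 0.064/1.16 = 0.0552 | 0.0554 | 80.0% |

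**5. Availability of later waves.** March to December 2016 is 12 − 3 = 9 months.

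**The case against.** The strongest case for the plan has four parts.

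- **T0 is the natural wave.** The programme aims to change all three constructs (Section 5.1), and T0 is the only wave before the three months of direct intervention. Section 6 describes no comparison group, although Section 7.2 calls the study randomised and controlled. Lagged paths would run through the intervention. Differing use of the platform, app and sessions could move well-being at T1 and eating attitudes at T2 together. This stands, and it is the reason to keep the T0 model.
- **The plan is open about the design.** Section 8.4 says of Study 2: "The manuscript will be a quantitative and transversal study and will focus on the relationships between food insecurity, well-being and disordered eating". A reader might infer an internal contradiction between the hypothesis and the analysis. The documents do not support that: the cross-sectional design is declared and no causal claim is written down. What remains is an analysis too weak for the hypothesis assigned to it.
- **T0 data are not uninformative.** A reader might infer that the T0 fit says nothing about the hypothesis. That goes too far. Absence of an indirect association would count against mediation, and a model without the direct path can be distinguished from the simple swap (step 2). The false-declaration rates in step 4 apply only to the model with a direct path, and the protocol does not say which will be fitted.
- **Lagging is no cure for confounding.** A reader might infer that confounding by SES requires the later waves. It does not, since SES can be adjusted for at T0. Nor does lagging remove unmeasured shared causes.

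Mediation also appears in no objective or endpoint in Section 5, so the evaluation of the programme in Study 5 is untouched. None of this lets one-wave data establish the order, and Section 8.4 still sets out to test mediation.

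**Conclusion.** The point holds in a limited form. Sections 4, 8.4 and 11.2 together fix the test of the second hypothesis as a T0-only structural model. Its result can be consistent with mediation or count against it, but cannot establish it.

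The equivalence of fit in steps 1 and 2 needs no assumed effect size. The numerical illustrations do: 0.113 against 0.140 rests on one assumed set of correlations, and the rates of about 11%, 36% and 80% rest on assumed paths of 0.2, 0.3 and 0.4, independent pupils and one score per construct. They show that the problem can be material, not how large it will be here.

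The change is worth making because a stated hypothesis depends on it. It does not bear on the primary endpoints.

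**What to change.** Amend Sections 8.4 and 11.2 as follows.

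1. Keep the T0 structural model as the pre-intervention analysis, adjusted for family SES. Report it as a cross-sectional association consistent, or not consistent, with mediation.
2. Add a lagged path model for the second hypothesis: food insecurity at T0, well-being at T1 and disordered eating at T2, adjusted for T0 well-being, T0 disordered eating and SES. Handle class with indicators or a small-cluster method, because ordinary cluster-robust errors are unreliable with only 12 classes.

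**Cost.** Analysis work and revised wording only. On the protocol's own dates there is no new data collection and no delay to the December 2016 submission. Precision will fall through attrition and because the model works on residual change. The protocol gives no attrition figure or between-wave correlations, so the loss cannot be sized. The lagged paths describe pupils receiving the programme. They supply temporal order, but unmeasured confounding and differing programme uptake remain and should be stated as limitations.

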### 3. Synopsis

The first United Nation's Millennium Development Goal is to eradicate extreme poverty and hunger. Following this objective, the European Union has been developing programs and funding research projects to assess and fight against food insecurity. WHO's European Food and Nutrition Action Plan (2015-2020) aims to reduce inequalities targeting vulnerable populations. In Portugal, the aim of the National Health Plan is to maximize health gains and to improve health in all individuals, reducing inequalities. Because of increasing autonomy that characterizes this life stage sometimes negatively influencing their eating patterns, sedentary life styles, and decreased financial resources of the families, adolescents are more likely to suffer from food insecurity. Furthermore, eating disorders are more likely to occur during adolescence and the literature has shown that both developmental tasks inherent to adolescence and pubertal changes, namely body changes, play here a key role.

Food insecurity, defined as limited or uncertain food accessibility, availability and quality, due to lack of resources, is a worldwide problem. The lack of valid epidemiological information to support decision-making constitutes a major public health challenge in Portugal. Moreover, there is a lack of management programs for adolescents targeting nutrition and well-being in order to optimize health status and reduce future co-morbidities.

Taking into account the principles above, we will conduct a longitudinal study with a mixed design, including 300 adolescents aged 12-14 years from two public schools. The intervention length is 6 months: (i) evaluation at baseline; (ii) 3 months of direct intervention; (iii) evaluation at month 3; (iv) follow-up at month 6. The intervention will include psycho-educative sessions directed to the adolescents and their parents. Furthermore, adolescents will have an access to the electronic platform and the

app developed by our team on purpose for this project, aiming to improve food security, psychological well-being, and prevent disordered eating among adolescents. The clinical endpoints will be: nutritional and physical status, well-being, and attitudes regarding eating.

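### The Study 2 mediation test, as described, names no family SES term, although Study 3 examines SES as an influence on the same three variables; the indirect effect may be confounded

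*Protocol*

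**What the plan says.** Protocol section 4 states two hypotheses. The second is that "psychological well-being variables mediate the relationship between food insecurity and disordered eating".

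Its test is Study 2, described in two places. In section 8.4, "The data collected in T0 will be used for the second manuscript", and the manuscript is cross-sectional. Section 11.2 says "we will perform structural equations modeling in order to analyze whether well-being is a mediator variable between food insecurity and disordered eating". Both places add sex as a moderator, and neither names another variable.

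Study 3 also uses T0 data. According to section 8.4 it "will focus on the impact of adolescents' family SES in food security, well-being and disordered eating". Section 11.2 gives it a separate multilevel analysis.

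The synopsis defines food insecurity as arising from a lack of resources. Among its reasons for concern about this age group it lists "decreased financial resources of the families, adolescents are more likely to suffer from food insecurity". Section 8.3 includes a socio-demographic questionnaire for the adolescents but does not describe its items.

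**The concern.** A mediation model attributes the association between exposure and mediator, and between mediator and outcome, to the paths that are drawn. A variable that influences exposure and mediator but is left out of the model creates an association that the model credits to the first path. Family SES is a candidate on the protocol's own terms. It is tied to food insecurity in the synopsis, and Study 3 asks about its impact on all three Study 2 constructs. Poorer families could have more food insecurity and lower well-being with no effect of one on the other, and the model would show an indirect effect.

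At stake is the reading of one of the two stated hypotheses: whether well-being carries the link from food insecurity to disordered eating, or whether part of that link is family resources. The problem is separate from temporal order and from clustering by class. It would remain if both were handled perfectly.

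**Working it through.** The protocol gives no effect size, correlation or power for Study 2, so there is no figure to reproduce. The check shows how large the confounding could be under stated assumptions.

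**Inputs.** n = 300 (section 11.1). Everything else is assumed: standardised variables, 5% two-sided tests, well-being to disordered eating b = -0.3, SES to disordered eating -0.2, and no true path from food insecurity to well-being. The SES effects on food insecurity (negative, size x) and on well-being (positive, size m) are varied. Mediation is declared when both paths are significant. Regressions on observed scores stand in for the structural equation model, and clustering is ignored.

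**Formula with SES omitted.** Write X for food insecurity, M for well-being and Y for disordered eating.
- First path: a* = r(XM) = -x·m
- r(MY) = -0.3 - 0.2m
- r(XY) = -0.3·r(XM) + 0.2x
- Second path: b* = [r(MY) - r(XM)·r(XY)] / [1 - r(XM)²]
- Spurious indirect effect = a*·b*

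For x = 0.4, m = 0.3:
- a* = -0.12
- r(MY) = -0.36
- r(XY) = 0.036 + 0.08 = 0.116
- b* = (-0.36 + 0.0139)/(1 - 0.0144) = -0.351
- indirect effect = 0.042, where the true value is 0

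**Simulated rate of false mediation** (3000 to 4000 data sets per setting, so Monte Carlo error is at most about 0.9 percentage points, from √(0.25/3000)):

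| x / m | a* | b* | Spurious indirect effect | SES omitted | SES included |
|---|---|---|---|---|---|
| 0.1 / 0.1 | -0.01 | -0.320 | 0.003 | about 6% | 4-6% |
| 0.2 / 0.2 | -0.04 | -0.338 | 0.014 | about 10% | 4-6% |
| 0.3 / 0.3 | -0.09 | -0.355 | 0.032 | about 33% | 4-6% |
| 0.4 / 0.3 | -0.12 | -0.351 | 0.042 | about 55% | 4-6% |
| 0.4 / 0.4 | -0.16 | -0.369 | 0.059 | about 79% | 4-6% |

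For scale, a real indirect effect built from paths of 0.2 and 0.3 in size would be 0.2 × 0.3 = 0.06.

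**What drives the result.**
- With the SES to disordered eating path set to zero, the rate is still about 55% at 0.4/0.3 and 34% at 0.3/0.3. A weak SES-outcome link does not protect the test.
- With no SES to well-being link, the rate stays at about 4-5%.
- If well-being truly has no effect on disordered eating, both paths must be spurious. With equal SES loadings L on all three variables, r = L² and the spurious indirect effect is r²/(1 + r). At L = 0.4 that is 0.0256/1.16 = 0.022. The false-mediation rates at L = 0.1, 0.2, 0.3, 0.4 and 0.5 are 0.4%, 1.4%, 10.8%, 53.3% and 93.6%. With SES included they are about 0.1-0.4%.
- If SES is measured with reliability 0.6, adjustment at 0.4/0.3 in the table's setting leaves about 14-16% false mediation, not 5%.

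**The case against.** The strongest objection is that silence is not exclusion. Section 11.2 gives Study 2 one sentence, and a covariate list may properly be left to an analysis plan that is not at hand. A reader might infer that the protocol rules SES out of the model. It does not, and an SES question in Study 3 does not bar SES from Study 2. What remains is narrower. The protocol describes this model twice, naming the moderator each time, and assigns the one confounder it raises itself to another manuscript.

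A reader might also infer that the protocol asserts SES as a cause of all three variables. It does not: Study 3 poses a question. Only the link to food insecurity is stated directly. For eating disorders the synopsis stresses developmental and pubertal change. The title of reference 13 reports an association of dysthymia and suicide symptoms with food insufficiency but not with low family income. Only the title is visible, but it points away from the SES to well-being link that the bias needs.

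Finally, every path value is assumed. That objection stands and limits the conclusion to a possibility. It does not remove the point, because SES effects of 0.3 on both variables already raise the error rate several-fold when well-being really does affect disordered eating.

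**Conclusion.** The point holds as a confounding risk that the described model leaves open. Whether it matters depends mainly on how strongly SES relates to both food insecurity and well-being. Under the assumptions above, with a real well-being path, false mediation runs from about 6% (effects of 0.1 each) to about 79% (0.4 each), against 4-6% with well-measured SES. If well-being has no effect on disordered eating, it runs from under 1% to over 90% across equal loadings of 0.1 to 0.5.

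The documents do not support saying that a shared SES correlation will be reported as mediation. They give none of these values, and a true indirect path may exist alongside the confounding. Bias away from zero also presumes the expected signs.

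The consequence is limited. Mediation is one of two hypotheses but is not among the objectives or endpoints in sections 5.1 to 5.5, and Study 5 is unaffected. The change is advisable because it is cheap, not because the trial depends on it.

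**What to change.** In section 11.2, state that the Study 2 model includes family SES from the T0 data as a covariate with paths to food insecurity, well-being and disordered eating. Name the SES-adjusted indirect effect as the test of hypothesis (ii), and report the unadjusted one beside it.

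BMI should not be added as a further covariate. Section 4 counts obesity within disordered eating and links food insecurity to overweight, so BMI may overlap the outcome or lie downstream of the exposure.

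The cost is one sentence and a few extra paths in AMOS. No new data are needed, since Study 3 already relies on SES at T0. The Study 2 and Study 3 manuscripts would overlap somewhat. The interval widens slightly: at 0.4/0.3 the standard error of the first path is proportional to √(0.91/0.84) = 1.04 with SES and to √(1 - 0.0144) = 0.99 without, about 5% more.

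The manuscript should also say what adjustment cannot do. It removes only SES as measured, and it cannot show that food insecurity precedes well-being, or well-being disordered eating, from data at a single time point.

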### 11. Statistical and analytical plan

### 11.1. Sample size

We expect to include 300 adolescents in the study (6 classes from each school).

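### The Study 5 repeated-measures ANOVA names no class effect, so tests of change over time are anti-conservative if the 12 classes change together; it also drops any pupil who misses a visit

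*Protocol*

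**What the plan says.** Protocol Section 11.2 sets the method for evaluating the programme: "in Study 5, we will conduct repeated-measures factorial ANOVASs for each variable", and "the analyses will be complemented with multiple comparisons using Bonferroni adjustment at p < .05". The software is SPSS and AMOS. Section 8.4 describes Study 5 as the quantitative longitudinal study of intervention impact using T0, T1 and T2, with a specific interest in the pupils classed as food insecure in Study 1. It therefore carries the primary endpoints of Section 5.4 and the first hypothesis of Section 4, all of which concern change from baseline at 3 and 6 months.

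Section 11.1 counts recruitment in classes: "We expect to include 300 adolescents in the study (6 classes from each school". Section 6 gives two schools. On delivery, Section 8.3 says: "In each classroom, an identification of the group leader will take place with the purpose of facilitating adherence". Section 8.2 plans group sessions, and Sections 6 and 8.3 have pupils discuss strategies with each other. For a different manuscript Section 11.2 says: "Multilevel analysis will be performed in Study 3". No class or school term is named for Study 5, and the protocol gives no ICC and no expected dropout.

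**The concern.** The programme is meant to work partly through peers: a leader in each classroom, group sessions and exchange of ideas among pupils. Classes could plausibly change together as a result of that mechanism. A repeated-measures ANOVA at pupil level treats 300 changes as independent. If changes are correlated within class, the standard error of the mean change is too small and the test of time rejects too often. Section 6 describes no comparison arm, so change over time is the main route to a claim of effect, and the time test is the one that has to be valid. The Bonferroni step does not help, because it adjusts p-values that are already too small.

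The same method, in its standard form, needs all three visits from each pupil. For food insecurity it needs all three parent questionnaires, since Section 8.3 has parents complete that instrument.

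**Working it through.** **Inputs from the protocol.** 300 adolescents and 6 classes per school (Section 11.1); two schools (Section 6); three visits (Section 6); nominal 0.05 (Section 11.2). Classes: 2 × 6 = 12. Mean class size: 300/12 = 25, which is derived, not stated. The 300 has no effect size, SD, power or ICC behind it, so there is no sample-size calculation to reproduce.

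**Assumptions.** The ICC here is that of the change (class-by-time), taken as 0.01 to 0.10. The missed-visit rate is taken as 5% to 20% per follow-up visit, independent between visits. The protocol gives neither.

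**Step 1: design effect for a mean change.** DE = 1 + (25 − 1) × ICC; effective n = 300/DE; actual error of one nominal two-sided 5% comparison of two visits = 2 × [1 − Φ(1.96/√DE)].

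| ICC of change | DE | Effective n | Actual error, two-visit comparison |
|---|---|---|---|
| 0.01 | 1.24 | 242 | 7.8% |
| 0.02 | 1.48 | 203 | 10.7% |
| 0.05 | 2.20 | 136 | 18.6% |
| 0.10 | 3.40 | 88 | 28.8% |

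**Step 2: simulated type I error.** 8,000 runs, 12 classes of 25, three visits, no true change. The time column is the repeated-measures F-test; the other two compare the T2−T0 change between groups.

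| Clustering | Time | School by time | Within-class factor by time |
|---|---|---|---|
| None | 0.051 | 0.053 | 0.048 |
| Class level only (intercept variance 0.1) | 0.054 | 0.051 | 0.048 |
| Class-by-time ICC 0.01 | 0.090 | 0.078 | 0.050 |
| 0.02 | 0.137 | 0.108 | 0.050 |
| 0.05 | 0.257 | 0.184 | 0.051 |
| 0.10 | 0.423 | 0.280 | 0.048 |

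A separate simulation of 4,000 runs gave 0.128 at ICC 0.02 and 0.262 at 0.05 for the time test, which agrees. The second row matters: stable class differences cancel within pupil. The last column has the form of a food-insecure-by-time test, and it is not inflated.

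**Step 3: pupils dropped.** Baseline is the entry assessment, so losses arise at two visits and the share kept is (1 − q)².

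- q = 5%: 0.9025, 271 kept, about 10% lost
- q = 10%: 0.81, 243 kept, 19% lost
- q = 15%: 0.7225, 217 kept, about 28% lost
- q = 20%: 0.64, 192 kept, 36% lost

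In records, at q = 10% the ANOVA uses 3 × 243 = 729 of the 300 × (1 + 2 × 0.9) = 840 collected; at q = 20% it uses 576 of 780.

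**Step 4: bias from dropping pupils.** Simulated with no true change, a correlation of 0.6 between visits and 10-20% dropout at T2. If dropout is completely at random there is no bias. If it depends on the T1 value (log odds ratio 0.5 to 1.0 per SD), complete-case bias is about −0.02 to −0.07 SD on T1−T0 and about 0 on T2−T0.

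**The case against.** The strongest reply is that the inflation is conditional. It requires classes to differ in their change, and the protocol gives no ICC. That stands, so the figures above are a range over assumptions. A reader might infer that every Study 5 p-value is too small. The documents do not support this, because level differences leave the time test near 5% and a food-insecure-by-time contrast is unaffected.

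Second, the planned ANOVA is described as factorial without listing its factors, so class or school could be intended as a between-subject factor, and Section 5.4 speaks of change among these adolescents. It is therefore right to say that no class term is named, not that none could be entered. A fixed class factor would still leave the error term at pupil level, so it would support conclusions about these 12 classes only.

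Third, 25 per class is derived. Section 6 says "About 300 community adolescents from two schools will be invited to participate in a study", and consent and assent are required, so enrolment of whole classes is not established. If, say, 60% joined (an assumption), there would be 15 per class, a DE of 1 + 14 × ICC = 1.28 to 1.70 at ICC 0.02-0.05, and a two-visit error of about 8% to 13%. The inflation is smaller but still present.

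Fourth, on missing visits, a reader might infer that the analysed sample is selected, with food-insecure households lost first. Nothing in the protocol shows this, and a missing-data rule may sit in a statistical analysis plan that is not shown. What follows from the stated method is loss of pupils and precision. One might also suppose that the breakfast, fast-food and family-meal indicators are yes/no or frequency items unsuited to ANOVA, but the protocol does not give their response formats.

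**Conclusion.** The point holds in conditional form. Section 11.2 fixes, for the only longitudinal evaluation of the intervention, a method with no named class effect, although recruitment is counted in 12 classes and delivery is partly class-based. If classes change together, tests of time, and of school by time, are anti-conservative. Even a class-by-time ICC of 0.01 takes a nominal 5% time test to about 9%, and 0.05 takes it to about 26%. These figures rest on assumed ICCs and on 25 pupils per class.

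The complete-case loss is a separate and secondary cost of the same choice. Its size depends on the assumed missed-visit rates, and bias arises only if missingness is related to outcome.

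**What to change.** In Section 11.2, replace the Study 5 ANOVA with a linear mixed model on all observed visits:

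- fixed effects: time, school (only two, so not random), baseline food-insecurity group, and food-insecurity group by time, which is needed for the aim stated in Section 8.4;
- random effects: class and class-by-time;
- a within-pupil covariance across the three visits;
- Satterthwaite or Kenward-Roger degrees of freedom, because there are only 12 classes.

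As a fallback for the overall change only, use a t-test on the 12 class-mean changes (11 df). This does not answer the food-insecurity comparison.

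**Cost.** Intervals for overall change widen by about √DE × (2.201/1.96): √1.48 × 1.12 = 1.4 at ICC 0.02 and √2.20 × 1.12 = 1.7 at ICC 0.05, where 2.201 is the two-sided 5% critical value on 11 df. If classes do not change together, the fallback costs only the factor of about 1.12. No new data are needed, provided each pupil's class is recorded at baseline.
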